APPENDIX A:

1. Acute GVHD organ staging

Stage	Skin	GI	Liver
1	< 25% rash	Diarrhea > 500ml/d or persistent nausea	Bilirubin 2-3mg/dl
2	25-50%	> 1000 ml/d	Bilirubin 3-6 mg/dl
3	> 50%	> 1500 ml/d	Bilirubin 6-15 mg/dl
4	Generalized erythroderma with bullae	Large volume diarrhea and severe abdominal pain ± ileus	Bilirubin > 15 mg/dl

Grade	Skin	GI	Liver
I	Stage 1-2	0	0
II	Stage 3 or	Stage 1 or	Stage 1
III	---	Stage 2-4	Stage 2-3
IV	Stage 4	---	Stage 4

2. Grading of Chronic GVHD (NIH Criteria)

	SCORE 0	SCORE 1	SCORE 2	SCORE 3
PERFORMANCE SCORE:  KPS ECOG LPS	 Asymptomatic and fully active (ECOG 0; KPS or LPS 100%)	 Symptomatic, fully ambulatory, restricted only in physically strenuous activity (ECOG 1, KPS or LPS 80-90%)	 Symptomatic, ambulatory, capable of self-care, >50% of waking hours out of bed (ECOG 2, KPS or LPS 60-70%)	 Symptomatic, limited self-care, >50% of waking hours in bed (ECOG 3-4, KPS or LPS <60%)
SKIN† SCORE % BSA  GVHD features to be scored by BSA: Check all that apply:  Maculopapular rash/erythema  Lichen planus-like features  Sclerotic features  Papulosquamous lesions or ichthyosis  Keratosis pilaris-like GVHD	 No BSA involved	 1-18% BSA	 19-50% BSA	 >50% BSA
SKIN FEATURES SCORE:	 No sclerotic features		 Superficial sclerotic features "not hidebound" (able to pinch)	Check all that apply:  Deep sclerotic features  "Hidebound" (unable to pinch)  Impaired mobility  Ulceration
Other skin GVHD features (NOT scored by BSA) Check all that apply:  Hyperpigmentation  Hypopigmentation  Poikiloderma  Severe or generalized pruritus  Hair involvement  Nail involvement  Abnormality present but explained entirely by non-GVHD documented cause (specify):				
MOUTH Lichen planus-like features present:  Yes  No  Abnormality present but explained entirely by non-GVHD documented cause (specify):	 No symptoms	 Mild symptoms with disease signs but not limiting oral intake significantly	 Moderate symptoms with disease signs with partial limitation of oral intake	 Severe symptoms with disease signs on examination with major limitation of oral intake

	SCORE 0	SCORE 1	SCORE 2	SCORE 3
EYES	 No symptoms	 Mild dry eye symptoms not affecting ADL (requirement of lubricant eye drops ≤ 3 x per day)	 Moderate dry eye symptoms partially affecting ADL (requiring lubricant eye drops > 3 x per day or punctal plugs), WITHOUT new vision impairment due to KCS	 Severe dry eye symptoms significantly affecting ADL (special eyewear to relieve pain) OR unable to work because of ocular symptoms OR loss of vision due to KCS
Keratoconjunctivitis sicca (KCS) confirmed by ophthalmologist:	 Yes  No  Not examined			
 Abnormality present but explained entirely by non-GVHD documented cause (specify):				
GI Tract	 No symptoms	 Symptoms without significant weight loss* ($< 5\%$)	 Symptoms associated with mild to moderate weight loss* (5-15%) OR moderate diarrhea without significant interference with daily living	 Symptoms associated with significant weight loss* $> 15\%$, requires nutritional supplement for most calorie needs OR esophageal dilation OR severe diarrhea with significant interference with daily living
Check all that apply:	 Esophageal web/proximal stricture or ring  Dysphagia  Anorexia  Nausea  Vomiting  Diarrhea  Weight loss $\geq 5\%*$  Failure to thrive			
 Abnormality present but explained entirely by non-GVHD documented cause (specify):				
LIVER	 Normal total bilirubin and ALT or AP < 3 x ULN	 Normal total bilirubin with ALT ≥ 3 to 5 x ULN or AP ≥ 3 x ULN	 Elevated total bilirubin but ≤ 3 mg/dL or ALT > 5 ULN	 Elevated total bilirubin > 3 mg/dL
 Abnormality present but explained entirely by non-GVHD documented cause (specify):				
LUNGS**	 No symptoms	 Mild symptoms (shortness of breath after climbing one flight of steps)	 Moderate symptoms (shortness of breath after walking on flat ground)	 Severe symptoms (shortness of breath at rest; requiring O ₂)
Symptom score:				
Lung score:	 FEV1 $\geq 80\%$	 FEV1 60-79%	 FEV1 40-59%	 FEV1 $\leq 39\%$
% FEV1 				
Pulmonary function tests				
 Not performed				
 Abnormality present but explained entirely by non-GVHD documented cause (specify):				

	SCORE 0	SCORE 1	SCORE 2	SCORE 3																																								
JOINTS AND FASCIA P-ROM score (see below) Shoulder (1-7): ___ Elbow (1-7): ___ Wrist/finger (1-7): ___ Ankle (1-4): ___	 No symptoms	 Mild tightness of arms or legs, normal or mild decreased range of motion (ROM) AND not affecting ADL	 Tightness of arms or legs OR joint contractures, erythema thought due to fasciitis, moderate decrease ROM AND mild to moderate limitation of ADL	 Contractures WITH significant decrease of ROM AND significant limitation of ADL (unable to tie shoes, button shirts, dress self etc.)																																								
 Abnormality present but explained entirely by non-GVHD documented cause (specify): _____																																												
GENITAL TRACT (See Supplemental figure[†])  Not examined Currently sexually active  Yes  No	 No signs	 Mild signs [†] and females with or without discomfort on exam	 Moderate signs [†] and may have symptoms with discomfort on exam	 Severe signs [†] with or without symptoms																																								
 Abnormality present but explained entirely by non-GVHD documented cause (specify): _____																																												
Other indicators, clinical features or complications related to chronic GVHD (check all that apply and assign a score to severity (0-3) based on functional impact where applicable none – 0, mild -1, moderate -2, severe – 3)																																												
 Ascites (serositis) ___  Myasthenia Gravis ___  Pericardial Effusion ___  Peripheral Neuropathy ___  Eosinophilia > 500/μl ___  Pleural Effusion(s) ___  Polymyositis ___  Platelets <100,000/μl ___  Nephrotic syndrome  Weight loss>5%* without GI symptoms  Others (specify): _____																																												
Overall GVHD Severity (Opinion of the evaluator)  No GVHD  Mild  Moderate  Severe																																												
Photographic Range of Motion (P-ROM)																																												

 
 	1 (Worst)	2	3	4	5	6	7 (Normal)	
 
 Shoulder								
 
 Elbow								
 
 Wrist/finger								
 
 Ankle								
 
						1 (Worst)	2	3	4	5	6	7 (Normal)	Shoulder								Elbow								Wrist/finger								Ankle							
	1 (Worst)	2	3	4	5	6	7 (Normal)																																					
Shoulder																																												
Elbow																																												
Wrist/finger																																												
Ankle																																												

3. Categories of Acute and Chronic GVHD

Categories of Acute and Chronic GVHD			
Category	Time of Symptoms after HCT	Presence of Acute GVHD Features	Presence of Chronic GVHD Features*
Acute GVHD			
Classic acute GVHD	≤100 d	Yes	No
Late-onset acute GVHD	>100 d	Yes	No
Chronic GVHD			
Classic chronic GVHD	No time limit	No	Yes
Overlap syndrome	No time limit	Yes	Yes

*as described herein:

Signs and Symptoms of Chronic GVHD

Organ or Site	Diagnostic (Sufficient to Establish the Diagnosis of Chronic GVHD)	Distinctive (Seen in Chronic GVHD, but Insufficient Alone to Establish a Diagnosis of Chronic GVHD)	Other Features*	Common (Seen with Both Acute and Chronic GVHD)
Skin	Poikiloderma	Depigmentation	Sweat impairment	Erythema
	Lichen planus-like features		Ichthyosis	Maculopapular rash

Organ or Site	Diagnostic (Sufficient to Establish the Diagnosis of Chronic GVHD)	Distinctive (Seen in Chronic GVHD, but Insufficient Alone to Establish a Diagnosis of Chronic GVHD)	Other Features*	Common (Seen with Both Acute and Chronic GVHD)
	Sclerotic features		Keratosi pilaris	Pruritus
	Morphea-like features		Hypopigmentation	
	Lichen sclerosis-like features		Hyperpigmentation	
Nails		
Dystrophy
 
Longitudinal ridging, splitting, or brittle features
 
Onycholysis
 
Pterygium unguis
 
Nail loss (usually symmetric; affects most nails)†
		

Organ or Site	Diagnostic (Sufficient to Establish the Diagnosis of Chronic GVHD)	Distinctive (Seen in Chronic GVHD, but Insufficient Alone to Establish a Diagnosis of Chronic GVHD)	Other Features*	Common (Seen with Both Acute and Chronic GVHD)
Scalp and body hair		New onset of scarring or nonscarring scalp alopecia (after recovery from chemoradiotherapy) Scaling, papulosquamous lesions	Thinning scalp hair, typically patchy, coarse, or dull (not explained by endocrine or other causes) Premature gray hair	
Mouth	Lichen-type features	Xerostomia		Gingivitis
	Hyperkeratotic plaques	Mucocoele		Mucositis
	Restriction of mouth opening from sclerosis	Mucosal atrophy Pseudomembranes† Ulcers†		Erythema Pain
Eyes		New onset dry, gritty, or painful eyes‡ Cicatricial conjunctivitis Keratoconjunctivitis sicca‡ Confluent areas of punctate keratopathy	Photophobia Periorbital hyperpigmentation	

Organ or Site	Diagnostic (Sufficient to Establish the Diagnosis of Chronic GVHD)	Distinctive (Seen in Chronic GVHD, but Insufficient Alone to Establish a Diagnosis of Chronic GVHD)	Other Features*	Common (Seen with Both Acute and Chronic GVHD)
Genitalia	
Lichen planus-like features
 
Vaginal scarring or stenosis
	
Erosions†
 
Fissures†
 
Ulcers†
	
Blepharitis (erythema of the eyelids with edema)
	
GI tract	
Esophageal web
 
Strictures or stenosis in the upper to mid third of the esophagus†
		
Exocrine pancreatic insufficiency
	
Anorexia
 
Nausea
 
Vomiting
 
Diarrhea
 
Weight loss
 
Failure to thrive (infants and children)

Organ or Site	Diagnostic (Sufficient to Establish the Diagnosis of Chronic GVHD)	Distinctive (Seen in Chronic GVHD, but Insufficient Alone to Establish a Diagnosis of Chronic GVHD)	Other Features*	Common (Seen with Both Acute and Chronic GVHD)
Liver				Total bilirubin, alkaline phosphatase >2 × upper limit of normal† ALT or AST >2 × upper limit of normal† BOOP
Lung	Bronchiolitis obliterans diagnosed with lung biopsy	Bronchiolitis obliterans diagnosed with PFTs and radiology‡		
Muscles, fascia, joints	Fasciitis Joint stiffness or contractures secondary to sclerosis	Myositis or polymyositis‡	Edema Muscle cramps Arthralgia or arthritis	
Hematopoietic and immune			Thrombocytopenia Eosinophilia	

Organ or Site	Diagnostic (Sufficient to Establish the Diagnosis of Chronic GVHD)	Distinctive (Seen in Chronic GVHD, but Insufficient Alone to Establish a Diagnosis of Chronic GVHD)	Other Features*	Common (Seen with Both Acute and Chronic GVHD)
Other			Lymphopenia	
			Hypo- or hypergammaglobulinemia	
			Autoantibodies (AIHA and ITP)	
			Pericardial or pleural effusions	
			Ascites	
			Peripheral neuropathy	
			Nephrotic syndrome	
			Myasthenia gravis	

Organ or Site	Diagnostic (Sufficient to Establish the Diagnosis of Chronic GVHD)	Distinctive (Seen in Chronic GVHD, but Insufficient Alone to Establish a Diagnosis of Chronic GVHD)	Other Features*	Common (Seen with Both Acute and Chronic GVHD)
			Cardiac conduction abnormality or cardiomyopathy	

GVHD indicates graft-versus-host disease; ALT, alanine aminotransferase; AST, aspartate aminotransferase; BOOP, bronchiolitis obliterans-organizing pneumonia; PFTs, pulmonary function tests; AIHA, autoimmune hemolytic anemia; ITP, idiopathic thrombocytopenic purpura.

* Can be acknowledged as part of the chronic GVHD symptomatology if the diagnosis is confirmed.

† In all cases, infection, drug effects, malignancy, or other causes must be excluded.

‡ Diagnosis of chronic GVHD requires biopsy or radiology confirmation (or Schirmer test for eyes).

Appendix B

General Guidance:

- In generally, medications listed in Table 1 should be avoided while medications listed in Tables 2 and 3 are to be used with caution when co-administered with PANO.
- It is of great importance to avoid combining drugs listed below in Table 1 and Table 2 (CYP3A inhibitors) especially in the presence of electrolyte abnormalities, notably decreased potassium or magnesium levels commonly associated with diuretic usage.

1 Medications which have a risk of causing Torsades de pointes ventricular arrhythmia should be avoided

Patients who are currently receiving treatment of the medications in Table 1 and cannot either discontinue from this treatment or switch to an alternative medication prior to enrollment, will be excluded from the study. Patients may not begin PANO treatment with any of the medications listed in Table 1 unless this is discussed with and approval is granted by Novartis. It may be agreed to temporarily discontinue PANO treatment (e.g., for 72 hours) during administration with these drugs or withheld medications in Table 1 for at least 72 hours when PANO is to be administered and missed dose(s) should be administered until completion of the trial specified PANO schedule.

This is not a comprehensive list of medications which may prolong the QT interval or have a risk of causing Torsades de pointes. This list of medications was developed in collaboration with an external cardiology consultant, and represents those medications which are deemed to have an unacceptable risk of co-administration with PANO.

The following website may be referenced as a supplemental guide for drugs which have been associated with Torsades de pointes or prolonging the QT interval but at this point lack substantial evidence for causing Torsades de pointes:

<http://www.qtdrugs.org/medical-pros/drug-lists/drug-lists.htm#>.

Medications listed on the website which do not appear in Table 1 may be used with caution at the discretion of the investigators.

The serotonin (5HT₃) antagonists, often used as antiemetics, such as ondansetron dolasetron, (also are known CYP2D6 substrates, see Table 3), or granisetron have been associated with Torsades de points and QT prolongation but have not been shown to cause Torsades de pointes. Therefore, 5HT₃ antagonists are not per se prohibited but close monitoring for signs and symptoms of QT prolongation is recommended. Caution is to be exercised when using these or other agents that may prolong QT intervals in combination with PANO.

Table 1. Medications which have a risk of causing Torsades de pointes to be avoided

All Class IA antiarrhythmics
 
 • quinidine • procainamide • disopyramide • any other class IA antiarrhythmic drug

All Class III antiarrhythmics
 
 amiodarone* sotalol bretylum disopyramide dofetilide ibutilide any other class III antiarrhythmic drug

Antibiotics
 
Macrolide antibiotics*
 
 • erythromycin • clarithromycin • telithromycin 
Quinolone antibiotics*
 
 sparfloxacin

Antipsychotics
 
 thioridazine mesoridazine chlorpromazine pimozide

Antimalarials
 
 • halofantrine • chloroquine

Miscellaneous drugs
 
 • arsenic trioxide • astemizole • bepridil • domperidone

 • levomethadyl • methadone • pentamidine IV* • droperidol

*Note: azithromycin, ciprofloxacin, levofloxacin, pefloxacin, ofloxacin, tosufloxacin, difloxacin, temafloxacin, fleroxacin, acrosoxacin, nalidixic acid and enoxacin are allowed. Inhaled pentamidine can be used for PCP prophylaxis (less likely to induce QTc prolongation). If amiodarone is used to the discretion of the treating physician, close monitoring of QTcF is recommended as clinically indicated.

2 Medications which are known strong CYP3A4/5 inhibitors to be used with caution Table 2.

Table 2 Medications which are known strong CYP3A4/5 inhibitors to be used with caution

Macrolide antibiotics*
 
 • clarithromycin • telithromycin • troleandomycin • erythromycin

Antifungals (azoles)*
 
 • ketoconazole • itraconazole • fluconazole

Antidepressants
 
 • nefazodone

Calcium channel blockers*
 
 • diltiazem • verapamil

HIV protease inhibitors:
 
 • indinavir • nelfinavir • ritonavir • saquinavir

Miscellaneous drugs or products
 
 • aprepitant

 grapefruit product or juice or grapefruit

* azithromycin, voriconazole, ketoconazole, regular orange juice and dihydropyridine calcium channel blockers (e.g. amlodipine, felodipine, nicardipine, nifedipine) are allowed.

This is not a comprehensive list of medications which may inhibit CYP3A4/5. Additional updated versions with moderate and weak CYP3A inhibitors, which are meant to be used as a guide, may be found at the following website: <http://medicine.iupui.edu/clinpharm/DDIs>

3 Medications which are known CYP2D6 substrates to be used with caution

Panobinostat was also shown to be a CYP2D6 inhibitor (K_i 0.17 μM) *in vitro*. Thus, clinical drug-drug interaction study with panobinostat as CYP2D6 inhibitor and dextromethorphan as CYP2D6 substrate was recently conducted in study [CLBH589B2109](#).

Multiple panobinostat doses increased C_{max} and AUC of dextromethorphan by a mean of 1.8- and 1.6-fold respectively, but with no change in T_{max} in 17 cancer patients. An approximately 2-fold increase in dextromethorphan AUC upon co-administration with panobinostat indicated that *in vivo* CYP2D6 inhibition of panobinostat is weak.

As the study was conducted using a sensitive CYP2D6 substrate which resulted in a weak inhibition, drugs with a large therapeutic index such as anti-emetics, anti-hypertensives, and anti-depressants are generally safe to be co-administered with panobinostat.

Patients should be carefully monitored for potential signs and symptoms of toxicity and may require dose titration or dose reduction of a sensitive CYP2D6 substrate which also have a narrow therapeutic window (e.g., the ratio of toxicity exposure is \leq 2-fold higher than the efficacious or therapeutic exposure).

Table 3-1 Medications which are known CYP2D6 substrates to be used with caution

Beta blockers (listed below):	Antipsychotics (listed below):
carvedilol	aripiprazole
metoprolol	haloperidol
propafenone	perphenazine
timolol	risperidone
Antidepressants (listed below):	thioridazine
amitriptyline	zuclopenthixol
chlormipramine	amphetamine
desipramine	alprenolol
imipramine	bufuralol

fluoxetine	chloropheniramine
paroxetine	Antiarrhythmics (listed below):
venlafaxine	quinidine
bupropion	lidocaine
duloxetine	mexiletine
Antiemetics (listed below):	propafenone
	Others:
	oxycodone
metoclopramide	codeine
	hydrocodone
	terbinafine
	promethazine
	tamoxifen
	Tramadol
Use of antiemetics ondansetron and dolasetron is contraindicated (granisetron use as an antiemetic is permitted).	

This is not a comprehensive list of CYP2D6 substrates. Additional updated versions of this list, which are meant to be used as a guide, may be found at the following website: <http://medicine.iupui.edu/clinpharm/DDIs> 1 Synold TW, Takimoto CH, Doroshow JH, Gandara D, Mani S, Remick SC, Mulkerin DL, Hamilton A, Sharma S, Ramanathan RK, Lenz HJ, Graham M, Longmate J, Kaufman BM, Ivy SP. Dose-Escalating and Pharmacological Study of Oxaliplatin in Adult Cancer Patients with Impaired Hepatic Function: A National Cancer Institute Organ Dysfunction Working Group Study, Clin Cancer Res. 2007 13; 3660

APPENDIX C. Study calendar for patients treated with TAC+SIR+PANO or with TAC+SIR (PANO has been discontinued due to GVHD)

Test and Procedures	Screening	-6/-5 ⁷	-1	+28	+60	+90	+120	+150	+180	+270	+365
				+/- 3days		+/- 14 days				+/- 30 days	
Medical history, complete physical exam, weight, vital signs, performance status by Karnofsky.	X			X	X	X	X	X	X	X	X
Transplant Vital organ testing. ¹	X										
BSA- Height.	X										
Consent signing	X										
TSH ⁴ , free T4 ⁴	X										X
Coagulation Profile (PT, PTT, Fibrinogen ⁴)	X										
PANO (PO) administration ⁵											
Electrocardiograms (EKGs) ²	X	X	X								
Biochemistries ³	X										
Cholesterol, LDL, HDL, triglycerides, and uric acid ⁴	X										
GVHD organ assessments				X	X	X	X	X	X	X	X
Record immune suppression				X	X	X	X	X	X	X	X
AE and SAE				X	X	X	X	X	X	X	X
Research Studies ⁶ (see Appendix F)											

¹ LVEF by MUGA and/or echocardiogram, PFT, CT chest, CT sinus, bone marrow, liver function tests, creatinine clearance, serum pregnancy test, infectious disease panel as per SOP. All must meet **inclusion criteria** detailed in body of protocol.

Exclusionary factors must be confirmed as negative upon screening evaluation, as detailed in the protocol.

² Electrocardiograms (EKGs): see section 5.6.

³ Biochemistry:: BUN, creatinine, sodium, potassium, chloride, CO₂ (HCO₃), glucose, calcium, albumin, total protein, total bilirubin, alkaline phosphatase, LDH, AST/SGOT, ALT/SGPT, phosphorous and magnesium, and uric acid. If total bilirubin is greater than the upper limit of normal, direct and indirect bilirubin should be performed. Biochemistry tests should be obtained after patient has fasted if possible.

⁴ test specific to study- cost covered by study budget

⁵PANO administration: Patients will be treated with PANO 5 MG PO TIW (3 doses about 48 hours apart in a 7 day period) QW for 26 weeks starting prior to stem cell infusion. See section 5.7.1.3 and Appendix G for further details.

⁶Research samples will be obtained on days-30 to -5, 15±3, 28±3, 90±14 and 365±45

⁷See Appendix G with details of PANO administration depending on conditioning regimen

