5.1.2. Umbilical cord blood and bone marrow stem cells are not an accepted stem cell source per this protocol.

5.2. **Conditioning regimen:** The conditioning regimen is per physician discretion and can include either 1) myeloablative (MAC) busulfan targeted at an AUC of $4800 \mu\text{M/L} \cdot \text{min/day}$ and fludarabine; 2) reduced-intensity (RIC) busulfan (6.4mg/kg total over 2 days or targeted at an AUC or $3500 \mu\text{M/L} \cdot \text{min/day}$) and Fludarabine; or 3) RIC fludarabine and melphalan (140mg/m^2). Busulfan targeted to an AUC of greater than $5,300\mu\text{M/L} \cdot \text{min/day}$ will not be allowed, given the concurrent administration of SIR, as this combination (escalated AUC of busulfan and sirolimus) was associated with increased risk for veno-occlusive disease (VOD) of the liver and non-relapse mortality in prior Moffitt trial (MCC 15372). Conditioning regimens/GVHD prophylaxis utilizing cyclophosphamide and/or anti-thymocyte globulin (ATG) as part of the conditioning regimen are not eligible.

5.3. **Supportive Care:** Transfusion as per institutional practice. Anti-infective prophylaxis or preemptive therapy as per institutional guidelines.

5.4. Antifungal Prophylactic Medications:

5.4.1. Micafungin is the preferred primary antifungal prophylaxis treatment given its minimal interaction with TAC and SIR metabolism.

5.4.2. Voriconazole or Posaconazole is allowed as per treating physician discretion.

5.4.3. Patients with presumed or proven pre-transplant infection treated with Voriconazole or Posaconazole will be allowed to continue with this treatment as it has been shown that for primary treatment of invasive aspergillosis, azoles like voriconazole have shown better responses and improved survival when compared to amphotericin B.⁴²

- 5.4.4. If patients develop GVHD (see section 6) on trial it is our standard practice to use voriconazole or posaconazole in patients receiving prednisone at a dose higher than 0.5mg/kg/day. In a randomized trial for prophylaxis against fungal infections among patients with GVHD, posaconazole was similar to fluconazole for prophylaxis against fungal infections among patients with GVHD; and posaconazole was superior in preventing invasive aspergillosis and reducing the rate of deaths related to fungal infections.⁴³

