- 5.5. **Other medications:** In general, the use of any concomitant medication/therapies deemed necessary for the care of the patient are allowed, including drugs given prophylactically (e.g. antiemetics) with the following precautions:
- 5.5.1. Any medications listed in Appendix B:
- 5.5.1.1. Which may cause QTcF prolongation or inducing torsades de pointes should not be used. Concomitant use of CYP3A4 inhibitors with PANO should be avoided to prevent potential increase in PANO exposure during concomitant treatment with these drugs.
- 5.5.1.2. Medications known to be substrates of the isoenzyme CYP2D6 should be avoided in use with PANO as this drug can inhibit isoenzyme CYP2D6 at low micromolar ranges. Please refer to Appendix B for the list of CYP2D6 substrates.
- 5.5.2. Patients receiving any medications that have the potential to alter serum electrolytes (e.g., diuretics) should be monitored very closely for electrolyte abnormalities as these can contribute to the risk of QT prolongation and ventricular arrhythmias.
- 5.5.3. No other investigational therapy should be given to patients during PANO administration or until toxicity related to PANO has not resolved.
- 5.5.4. Leukocyte growth factors (e.g.G-CSF and GM-CSF) are not to be administered systematically but may be prescribed for ANC < 750 per microliter if this is thought to be appropriate.
- 5.5.5. Ursodiol is allowed as per institutional guidelines at any time during this trial.
- 5.5.6. Budesonide and beclomethasone. For patients with gastrointestinal GVHD, budesonide and/or beclomethasone, with or without systemic corticosteroids are allowed.

5.6. EKG monitoring:

- 5.6.1. **Screening.** One 12-lead EKGs will be performed to assess study eligibility at time of enrollment to accurately estimate Fridericia correction for QTC (QTcF) calculation as listed in Table 4 which is available in MUSE system. If EKG QTcF is above 480msec a minimum of 3 sequential 12 lead EKGs, separated by at least 2 minutes, must be performed. The QTcF, or average of 3, (at baseline must be ≤ 480 msec for the patient to be **eligible** for participation in the trial). The EKG will be analyzed by the treating physician or principal investigator or designee to assess eligibility of the patient.
- 5.6.2. Additional 12-lead EKGs will be performed at a minimum at scheduled time points as indicated in Table 4 as follows:
- 5.6.2.1. With 1st dose: Pre-dose EKG and post dose EKG
- 5.6.2.2. With 3rd dose: Pre-dose EKG

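### Appendix B gives ondansetron and dolasetron two opposite statuses with PANO, and its CYP3A4 wording does not match section 5.5.1.1

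*Combined protocol and SAP*

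**What the plan says.** **Antiemetics.** Appendix B, section 1, discusses 5HT3 antagonists, "often used as antiemetics, such as ondansetron dolasetron, (also are known CYP2D6 substrates, see Table 3), or granisetron". It notes their association with QT prolongation and concludes that 5HT3 "antagonists are not per se prohibited but close monitoring for signs and symptoms of QT prolongation is recommended". The footnote to Table 3-1 in the same appendix reads: "Use of antiemetics ondansetron and dolasetron is contraindicated (granisetron use as an antiemetic is permitted". The text above that table adds that "drugs with a large therapeutic index such as anti-emetics, anti-hypertensives, and anti-depressants are generally safe to be co-administered with panobinostat".

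**CYP3A4 inhibitors.** Section 5.5.1.1 states: "Concomitant use of CYP3A4 inhibitors with PANO should be avoided". The reason given is a possible rise in PANO exposure, and no exception is written there. The general guidance in Appendix B says "medications listed in Tables 2 and 3 are to be used with caution when co-administered with PANO"; Table 2 is the list of strong CYP3A4/5 inhibitors, and its heading repeats the caution wording. On antifungals, section 5.4.2 states: "Voriconazole or Posaconazole is allowed as per treating physician discretion". Section 5.7.1.1.2 also provides for these two azoles in active fungal infection and with corticosteroids at or above 0.5 mg/kg/day. The Table 2 footnote allows voriconazole.

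**The concern.** A prescriber who reads section 1 of Appendix B may give ondansetron or dolasetron with monitoring. One who reads the Table 3-1 footnote may not give either. Both are following the protocol. Section 1 treats the matter as one of QT risk. The footnote gives no reason and sits under a table of CYP2D6 substrates, so the reader cannot tell whether it is meant to override section 1.

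What is at stake is mainly patient safety and consistent conduct. The same text also bears on entry to the trial: exclusion 4.2.9.7 removes patients whose QT-prolonging drugs cannot be stopped or switched, but exempts Appendix B drugs that transplant patients require. If Appendix B does not give a drug one status, that exemption is unclear for it.

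The CYP3A4 wording matters for a different reason. Section 1.8 states that oxidative metabolism of PANO is mainly by CYP3A4, so two different instructions on inhibitors could mean different PANO exposure for similar patients.

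**Working it through.** No calculated figure is involved, so the check is a comparison of the passages.

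| Topic | Place | Instruction |
|---|---|---|
| Ondansetron, dolasetron | Appendix B, section 1 | Not prohibited; close QT monitoring |
| Ondansetron, dolasetron | Appendix B, Table 3-1 footnote | Contraindicated |
| Granisetron | Both of these places | May be used |
| CYP3A4 inhibitors | Section 5.5.1.1 | Avoid; no exception stated |
| Strong CYP3A4/5 inhibitors | Appendix B, general guidance and Table 2 | Use with caution |
| Voriconazole, posaconazole | Sections 5.4 and 5.7.1.1.2 | Permitted |

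**1. Can both antiemetic statements be true?** For granisetron, yes. For ondansetron and dolasetron, no: the same two drugs, with the same study drug, in the same appendix, are not prohibited in one place and contraindicated in the other.

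**2. Does any other passage settle it?** No.
- The first sentence of section 5.5.1.1 says of Appendix B drugs: "Which may cause QTcF prolongation or inducing torsades de pointes should not be used". Taken literally this could also reach granisetron, which both Appendix B passages permit.
- The remark that antiemetics are generally safe comes from the CYP2D6 interaction result and does not address QT.
- The general guidance puts Table 3 drugs in the caution category, which is not the footnote's category for these two drugs.

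**3. Will clinicians meet the conflict?** Yes. Section 5.5 names antiemetics as an example of prophylactic drugs. Section 8.9 asks that antiemetics be considered before PANO is modified, and Table 7 makes a hold for grade 3 nausea or vomiting depend on their failure. Appendix G places the first PANO dose on day -6 or -5, together with conditioning chemotherapy.

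**4. What does the monitoring condition rest on?** Section 5.6 schedules EKGs, as a minimum, at screening, before and after the first dose, and before the third dose. The planned course is 3 doses a week for 26 weeks, that is 3 × 26 = 78 doses. No EKG is scheduled for the remaining 78 − 3 = 75, although more may be done. The written drug status therefore carries more weight later in the course.

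**5. CYP3A4 inhibitors.** Avoiding a class and using its strong members with caution are different instructions. The azole permissions read as deliberate exceptions, but section 5.5.1.1 neither states nor cross-refers to them. Overlap with PANO is possible by the protocol's own rules: section 5.7.1.1.2 brings in an azole from 0.5 mg/kg/day of corticosteroid, while section 6.3 stops PANO for GVHD that needs 1-2 mg/kg.

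**The case against.** **Class rule and specific exception.** Section 1 of Appendix B speaks of a drug class and refers the reader to Table 3, where the drug-specific footnote sits. The footnote could be read as a restriction on a general permission. This softens the conflict but does not remove it. The reference to Table 3 is attached to CYP2D6 substrate status, not to a prohibition, and section 1 names both drugs as examples and draws the same conclusion for them as for granisetron.

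**QTcF limits protect the patient anyway.** Dosing decisions in section 5.6 depend on measured QTcF, whatever the co-medication, with repeat EKGs and electrolyte correction. That is a real, partial safeguard. A reader might infer that QTcF holds will vary with the page followed; the documents do not show this. The limit of the safeguard is that scheduled EKGs end at the third dose.

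**The CYP3A4 text is general rule versus specific permission.** Section 5.5 opens by allowing necessary concomitant drugs with precautions, and advice to avoid is not a ban. For voriconazole and posaconazole a prescriber finds an explicit answer. This largely stands and is why the CYP3A4 part is secondary. What remains is the unmatched wording between section 5.5.1.1 and Appendix B for the other strong inhibitors.

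**Individual azoles.** A reader might infer a further contradiction because posaconazole is missing from the Table 2 footnote. It is not on the Table 2 list either, that list is described as incomplete, and section 5.4.2 permits the drug by name, so nothing conflicts. Ketoconazole appears both on the caution list and as allowed; those two statements are compatible.

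**Conclusion.** The contradiction on ondansetron and dolasetron is real and is wrong as written. It should be corrected because it concerns a safety instruction that clinicians will need from the first doses. The CYP3A4 wording is a lesser inconsistency to be aligned in the same edit.

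The size cannot be stated as a number. The documents give no expected use of either antiemetic, so between 0 and 44 planned treated patients could be affected. The 20 external controls receive no PANO. Sample size, error rates and the primary analysis are untouched.

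Two stronger readings are tempting and are not supported:

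- A reader might infer that azoles will be used in most patients when PANO starts, perhaps from section 1.4, where 14 patients in the PANO treatment study had voriconazole and 5 micafungin. That study treated established acute GVHD, with PANO started within 72 hours of glucocorticoids. Here micafungin is the preferred primary prophylaxis (sections 5.4.1 and 5.7.1.1.2), so the split does not carry over.
- A reader might infer that different centres would follow different rules. Section 3.2 names one site; the conflict falls on its physicians and pharmacists.

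The QT link is direct for the antiemetics through section 1 of Appendix B. For CYP3A4 inhibitors, section 5.5.1.1 argues from exposure only; QT enters through the general guidance against combining Table 1 and Table 2 drugs.

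**What to change.** 1. Reconcile section 1 of Appendix B with the Table 3-1 footnote so that ondansetron and dolasetron have one status, with the reason stated.
2. Align section 5.5.1.1 with the general guidance and Table 2 of Appendix B, and cross-refer to the azole permission in sections 5.4 and 5.7.1.1.2. One rule with cross-references is enough; it need not be repeated in every section.

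Which status and which rule apply is for the sponsor's clinical and safety team. The cost is a text clarification. If it is treated as more than administrative, section 11.5 requires a written amendment with review by the drug supplier and the IRB. No visit, sample, data item or analysis changes.
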